6.3.2. Etrasimod micro sampling concentration

The micro sampling will be performed in this study, but the results of analyzing this data will not be included in the CSR. Instead, a separate internal bioanalytical report will be issued to document data and conclusions from this analysis. However, *etrasimod concentration at sampling time points*, C_{max} and AUC_{0-24} from paired samples obtained via micro sampling and venous sampling will be compared. Individual participant differences and % differences

DMB02-GSOP-RF02 7.0 Statistical Analysis Plan Template 31-Jan-2022 PFIZER CONFIDENTIAL TMF Doc ID: 98.03 Page 14 of 20 of concentrations by PK sampling time, C_{max} and AUC_{0-24} will be listed and summarized descriptively.

6.4. Subset Analyses

There are no planned subset analyses.

6.5. Baseline and Other Summaries and Analyses

6.5.1. Demographic Summaries

Demographic characteristics will be summarized for Safety Analysis Set in accordance with the CaPS.

6.5.2. Study Conduct and Participant Disposition

Participants evaluation groups will show end of study participant disposition. Frequency counts will be supplied for participant discontinuation(s) by treatment. Data will be reported in accordance with the CaPS.

6.5.3. Study Treatment Exposure

Study treatment exposure will be listed.

6.5.4. Concomitant Medications and Nondrug Treatments

All prior and concomitant medication(s) as well as non-drug treatment(s) will be reported in the listings.

6.6. Safety Summaries and Analyses

All safety analyses will be performed on the Safety Analysis Set.

Safety data will be presented in tabular and/or graphical format and summarized descriptively, where appropriate.

6.6.1. First Dose HR reduction

Changes from predose baseline in HR at every hour up to 6 hours, at 8 and 24 hours on Day 1, as well as the nadir HR value on Day 1, will be summarized by treatment.

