# 2.2.4.2. Safety Overview of Etrasimod

As of 30 Aug 2022, a total of 2119 participants (419 healthy participants and 1700 participants with disease) have been exposed to etrasimod in clinical development programs. Clinical evidence in participants of healthy status, UC, CD, AD, AA or EoE to date have demonstrated that etrasimod is well tolerated in humans.

Across all clinical studies (Phase 1 to Phase 3), etrasimod caused expected mild, transient, and generally asymptomatic reduction in HR at first dose and very few participants with HR < 50 bpm. These reductions were greatest following first dose and lessened upon repeat dosing due to development of tolerance, allowing HR to return to baseline. The HR effects are related to S1P1 localized on atrial myocytes that activate GIRK channels, which are transient and not clinically adverse or associated with safety findings.

Etrasimod 2 mg administered once daily demonstrated an acceptable safety profile up to 52 weeks in controlled studies and up to 104 weeks in uncontrolled studies. There was a low incidence of SDEIs such as infections, including severe (ie, Grade  $\geq$ 3) infections, opportunistic infections, and herpes infections (herpes zoster and herpes simplex), cardiac

safety events (bradycardia, AV conduction delays, and hypertension), malignancies, liver injury (liver transaminase elevation and bilirubin elevation), macular oedema, and pulmonary disorders (airflow obstruction and decreased gas exchange) in participants who were treated with etrasimod 2 mg.

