# **3. OBJECTIVES AND ENDPOINTS**

Objectives	Endpoints
Primary:	Primary:

 
To estimate the rBA of etrasimod 2 mg mini tablets mixed with water compared to etrasimod 2 mg clinical IR tablets under fasted conditions
 
To estimate the rBA of the etrasimod 2 mg mini tablets mixed with applesauce compared to the etrasimod 2 mg clinical IR tablets under fasted conditions
 
To estimate the rBA of the etrasimod 2 mg mini tablets mixed with chocolate pudding compared to the etrasimod 2 mg clinical IR tablets under fasted conditions
 
To estimate the rBA of the etrasimod 2 mg mini tablets mixed with chocolate pudding compared to the etrasimod 2 mg clinical IR tablets under fasted conditions
 
To estimate the rBA of the etrasimod 2 mg mini tablets mixed with yogurt compared to the etrasimod 2 mg clinical IR tablets under fasted conditions
 
	• Plasma AUC last , AUC inf and C max of etrasimod
Secondary:	Secondary:
• To evaluate the safety and tolerability of etrasimod in healthy participants	• Assessment of first dose HR reduction, TEAEs, clinical laboratory abnormalities, vital signs, PEs, and 12-lead ECGs
• To assess the palatability of etrasimod mini tablets mixed with water/applesauce/chocolate pudding/yogurt	• Assessment of palatability via questionnaire: mouth feel, bitterness, tongue/mouth burns, throat burn, and overall liking
Tertiary/Exploratory:	Tertiary/Exploratory:
• To characterize the PK parameters of etrasimod 2 mg mini tablets mixed with water or soft foods (applesauce, chocolate pudding, or yogurt) compared to etrasimod 2 mg clinical IR tablet	
 
Plasma etrasimod: t1/2, CL/F, Vz/F and Tmax of etrasimod
 

• To validate the PK measurement of etrasimod in capillary blood sample collected using micro sampling device against the PK measurement of etrasimod in venous blood samples.	• Plasma concentration of etrasimod obtained via micro sampling compared to venous sampling

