### 4. STUDY DESIGN

### 4.1. Overall Design

This is a Phase 1, open-label, single-dose, randomized 4-crossover periods and 1-fixed period design in a single cohort of approximately 16 healthy male or female participants .

The study will consist of 5 treatments as shown below:

- 1. Treatment A: Single oral dose of etrasimod 2 mg clinical IR tablet under fasted conditions (Reference)
- 2. Treatment B: Single oral dose of etrasimod 2 mg mini tablets mixed with applesauce under fasted conditions (Test 1)
- 3. Treatment C: Single oral dose of etrasimod 2 mg mini tablets mixed with chocolate pudding under fasted conditions (Test 2)
- 4. Treatment D: Single oral dose of etrasimod 2 mg mini tablets mixed with water under fasted conditions (Test 3)
- 5. Treatment E: Single oral dose of etrasimod 2 mg mini tablets mixed with yogurt under fasted conditions (Test 4)

Sixteen participants will be enrolled in Period 1 for a total of 12 evaluable participants to complete study. Participants will be randomly assigned to 1 of the 4 sequences shown in Table 2 in which participants are randomized in crossover design to receive Treatments A to D in Periods 1 to 4 with Treatment E being fixed in Period 5. Participants will be discharged on Day 9 of Period 5, following completion of all assessments. Each treatment is 9 days that includes dosing, PK sampling and an extra day to minimize any residual etrasimod concentrations prior to start of the next treatment. The total planned duration of participation from the screening visit to the last follow-up phone call, is approximately 14 weeks.

Treatment sequence (n=4 per sequence)	Period 1	Period 2	Period 3	Period 4	Period 5 (fixed)
1	А	В	С	D	Е
2	В	D	А	С	Е
3	С	А	D	В	Е
4	D	С	В	А	Е

 Table 2.
 Treatment Sequence

Since etrasimod has a half-life approximately 30 hours, there will be a 9-day washout between each dose.

Blood samples for PK analysis will be collected predose and at 1, 2, 4, 6, 8, 12, 24, 48, 72, 96, 120, 144 and 168 hours postdose (SoA). Capillary blood samples (using micro sampling Tasso device) will be collected at predose and at 1, 2, 4, 6, 8, 12 and 24 hours postdose (SoA) for PK assessments (Treatment A). Micro PK sampling occurs after PK blood sampling, and taken from the other arm.

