# 6.9. Prior and Concomitant Therapy

Use of prescription or nonprescription drugs and dietary and herbal supplements are prohibited within 7 days or 5 half-lives (whichever is longer) prior to the first dose of study

intervention. Limited use of nonprescription medications that are not believed to affect participant safety or the overall results of the study may be permitted on a case-by-case basis following approval by the sponsor. Acetaminophen/paracetamol may be used at doses of  $\leq 2$  g/day.

Hormonal contraceptives that meet the requirements of this study are allowed to be used in participants who are WOCBP (see Appendix 4). Postmenopausal hormonal therapy is allowed.

All concomitant treatments taken during the study must be recorded with indication, daily dose, and start and stop dates of administration. All participants will be questioned about concomitant treatment at each clinic visit.

Treatments taken within 28 days before the first dose of study intervention will be documented as a prior treatment. Treatments taken after the first dose of study intervention will be documented as concomitant treatments.

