3.5.1. First Dose HR reduction

For all periods, HR will be measured every hour up to 6 hours, at 8 and 24 hours postetrasimod dose at Day 1. The baseline HR value is the average of the HR values from the triplicate ECG measurements collected predose on Day 1 of each period. Changes from baseline will be defined as the change between the postdose measurements and baseline value. In addition, the nadir HR value on Day 1 will be derived.

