3.5.5. Electrocardiograms

QT interval, QTcF, PR interval, QRS and heart rate (HR) will be recorded at each 12-lead ECG assessment time indicated in the SoA given in the protocol. QTcF will be derived using Fridericia's heart rate correction formula:

 $QTcF = QT / (RR)^{(1/3)}$ where RR = 60/HR (if not provided)

For all periods, the baseline value is the average of triplicate ECG measurements collected predose on Day 1 of each period. Changes from baseline will be defined as the change between the postdose measurements and baseline value.

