6.6.5. Electrocardiograms

ECG data will be listed and summarized by treatment in accordance with the CaPS.

Changes from baseline for the ECG parameters will be summarized by treatment. The number (%) of participants with maximum postdose QTcF values and maximum increases from baseline in the following categories will be tabulated by treatment.

Degree of Prolongation	Mild (ms)	Moderate (ms)	Severe (ms)
Absolute value	>450 - 480	>480 - 500	>500
Increase from baseline		30-60	>60

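### SAP 6.6.1 summarises first-dose heart rate reduction by treatment only: 4 of 16 values for each of Treatments A to D and none for E follow a first etrasimod dose, and no Period 1 or by-period summary is planned

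*SAP*

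**What the plan says.** Protocol Section 3 (repeated in SAP 2.2) gives the secondary safety endpoint as "Assessment of first dose HR reduction, TEAEs, clinical laboratory abnormalities, vital signs, PEs, and 12-lead ECGs". First-dose HR reduction is thus listed apart from vital signs and ECGs.

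Protocol 2.2.4.2 describes the effect across the clinical programme: "These reductions were greatest following first dose and lessened upon repeat dosing due to development of tolerance, allowing HR to return to baseline".

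Protocol 4.1 has participants "randomized in crossover design to receive Treatments A to D in Periods 1 to 4 with Treatment E being fixed in Period 5". There are four sequences of four participants, one dose per period, and 9 days between doses.

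SAP 3.5.1, headed First Dose HR reduction, sets the data source: "For all periods, HR will be measured every hour up to 6 hours, at 8 and 24 hours" after the Day 1 dose. Baseline is the predose triplicate ECG average, taken afresh in each period. SAP 6.6.1 then has the changes from baseline, "as well as the nadir HR value on Day 1, will be summarized by treatment".

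Two other SAP sections also produce HR or pulse rate summaries, both by treatment: 6.6.4 for vital signs and 6.6.5 for ECGs. SAP 6.4 plans no subset analyses.

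**The concern.** On the ordinary reading, first-dose HR reduction is the change after a participant's first exposure to etrasimod, and the protocol itself says the effect is largest then. A table that combines Day 1 of all periods within each treatment does not isolate that quantity. Its Treatment E column would carry a first-dose title while holding only fifth doses.

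First-dose HR slowing is the class effect that this study's hourly monitoring is there to watch, and Protocol 2.3 says the study is meant to supply mini tablet safety data for future pediatric studies. A reader of the study report who wants the size of the first-dose reduction would find no summary of it. That reader would also find no by-period display to show whether later doses behave like first ones. No PK result is involved.

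**Working it through.** **Inputs.** Sequences, from Table 2 in both documents: ABCDE, BDACE, CADBE, DCBAE, with 4 participants each. Half-life of about 30 hours and a 9-day interval (Protocol 4.1, SAP 2.3).

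**1. Planned sample size.** 4 sequences × 4 participants = 16, which matches the stated total.

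**2. First doses per treatment.** Counting participants by treatment and period:

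| Treatment | P1 | P2 | P3 | P4 | P5 | First doses |
|---|---|---|---|---|---|---|
| A | 4 | 4 | 4 | 4 | 0 | 4/16 = 25% |
| B | 4 | 4 | 4 | 4 | 0 | 4/16 = 25% |
| C | 4 | 4 | 4 | 4 | 0 | 4/16 = 25% |
| D | 4 | 4 | 4 | 4 | 0 | 4/16 = 25% |
| E | 0 | 0 | 0 | 0 | 16 | 0/16 = 0% |

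Planned Day 1 profiles: 16 × 5 = 80. First doses: 4 × 4 + 0 = 16, or 16/80 = 20%. The other 64 (80%) are later doses. Dropout or replacement could shift the denominators. E would still hold no first doses, because it comes after Periods 1 to 4 in every sequence.

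**3. Is the first dose isolated elsewhere?** SAP 3.5.5 states that "QT interval, QTcF, PR interval, QRS and heart rate (HR) will be recorded at each 12-lead ECG assessment time", and SAP 6.6.5 that "Changes from baseline for the ECG parameters will be summarized by treatment". HR change by treatment is therefore already produced there; 6.6.1 adds the nadir. Pulse rate in 6.6.4 is also by treatment, and 6.4 rules out planned subsets. Neither document specifies a Period 1 or by-period HR summary.

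**4. What the protocol means by the first dose.**
- Pointing to Period 1: Section 6.9 states "Treatments taken after the first dose of study intervention will be documented as concomitant treatments", which makes sense only for the first dose in the study. Section 2.2.4.2 contrasts the first dose with repeat dosing.
- Pointing to each period: the risk table in Section 2.3.1, under the first-dose cardiac effect, provides for hourly HR monitoring over 6 hours after the first dose in all dosing periods. SAP 3.5.1 resets the baseline in every period.

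The term is not defined, and both readings have support.

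**5. Illustrative size, not an estimate.** Let r be the mean HR reduction after doses 2 to 5 as a fraction of the mean first-dose reduction. The documents give no value for r. Assume one r for all later doses, no vehicle effect and no dropout. The mean change shown, as a fraction of the first-dose reduction, is:
- A to D: (4 × 1 + 12 × r)/16 = (1 + 3r)/4
- E: r
- A to D minus E: (1 + 3r)/4 − r = (1 − r)/4

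| r | A to D | E | Difference |
|---|---|---|---|
| 1 | 100% | 100% | 0 |
| 0.75 | 81.25% | 75% | 6.25 points |
| 0.5 | 62.5% | 50% | 12.5 points |
| 0.25 | 43.75% | 25% | 18.75 points |
| 0 | 25% | 0% | 25 points |

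The last row is a mathematical bound. Nothing in the documents suggests complete tolerance after one dose.

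**6. Drug left at the next dose.** 9 × 24 = 216 hours; 216/30 = 7.2 half-lives; 0.5^7.2 = 0.0068, or about 0.7%. Residual drug is negligible. This says nothing directly about how fast HR sensitivity recovers.

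**The case against.** The strongest reply is that protocol and SAP agree. In the cardiac context, Section 2.3.1 extends first-dose monitoring to every period, and the SAP follows with a fresh baseline each time. If each single dose after washout counts as a first dose, 6.6.1 summarises what was intended. The tolerance statement in 2.2.4.2 covers the whole programme, including once-daily dosing, while here single doses are 7.2 half-lives apart. Section 2.3.1 also reports that lymphocyte counts return to the normal range by Day 7 after a single dose. A by-treatment display suits a study that compares formulations descriptively, and ECG data will be listed, so Period 1 values can be recovered.

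Much of this stands. A reader might infer that the SAP contradicts the protocol. The documents do not support that, because the term is ambiguous and one reading fits the SAP. A reader might also infer that the pooled table will understate the first-dose reduction, or make the yogurt treatment look gentler than the others. That needs tolerance to persist over 9 days, and nothing in either document says it does. Separately, Treatment E coincides with Period 5 by design for every endpoint. This is not a fault of 6.6.1, and no change of table removes it.

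Three parts of the reply do not settle the matter. Each period has exactly one dose, so under the each-period reading the word first distinguishes nothing, and 6.6.1 adds only the nadir to 6.6.5. Drug washout and lymphocyte recovery are not evidence that HR sensitivity recovers. Listings permit a hand extraction but are not a planned summary. The sponsor's reporting standards, which the SAP cites but which are not supplied, may add displays; that cannot be checked here.

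**Conclusion.** The point holds as a minor gap in a descriptive safety summary, not as an inconsistency between the documents. The counts are exact under the planned design: 4 of 16 for each of A to D, 0 of 16 for E, and 16 of 80 overall. No specified summary shows HR change for Period 1 or by period.

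The practical effect is unknown. It is nil if the HR response recovers fully between doses (r = 1) and grows as r falls, under the assumptions of a common r, no vehicle effect and no dropout. Confidence is medium, because the point rests on reading first dose as the Period 1 dose. That is the ordinary reading, but not the only one the protocol allows.

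**What to change.** In SAP 3.5.1, define first-dose HR reduction as the change from predose baseline in HR after the Period 1 dose.

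In SAP 6.6.1, summarise the changes at each hour to 6 hours, at 8 and 24 hours, and the nadir:
- for Period 1 overall (n=16);
- by period;
- by treatment over all periods, as now, but headed *HR change after dosing, all periods*.

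A split of Period 1 by treatment is optional, since it has only 4 participants per cell. The by-period table gives a descriptive view of whether later doses resemble the first, with one caution: Period 5 is entirely Treatment E. If the response looks stable over periods, that would support the each-period reading.

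The cost is one added sentence, one replaced sentence and two more descriptive tables from data already scheduled. No new assessment and no protocol amendment are needed, and the change can be made before database lock.

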6.6.2. Adverse Events

AEs will be reported in accordance with the CaPS.

Participant discontinuations due to adverse events will be detailed by treatment. Data will be reported in accordance with the CaPS.

6.6.3. Laboratory Data

Laboratory data will be listed and summarized by treatment in accordance with the CaPS.

DMB02-GSOP-RF02 7.0 Statistical Analysis Plan Template 31-Jan-2022 PFIZER CONFIDENTIAL TMF Doc ID: 98.03 Page 15 of 20

6.6.4. Vital Signs

Vital sign data will be listed and summarized by treatment in accordance with the CaPS.

6.6.5. Electrocardiograms

ECG data will be listed and summarized by treatment in accordance with the CaPS.

Changes from baseline for the ECG parameters will be summarized by treatment. The number (%) of participants with maximum postdose QTcF values and maximum increases from baseline in the following categories will be tabulated by treatment.

Degree of Prolongation	Mild (ms)	Moderate (ms)	Severe (ms)
Absolute value	>450 - 480	>480 - 500	>500
Increase from baseline		30-60	>60

7. INTERIM ANALYSES

No formal interim analysis will be conducted for this study. As this is an open-label study, the sponsor may conduct unblinded reviews of the data during the course of the study for the purpose of safety assessment, facilitating PK/PD modeling, and/or supporting clinical development.

Final analysis will follow the official database release. As this will be an open-label study, there is no formal unblinding of the randomization code.

APPENDICES

Appendix 1. SAS Code for Analyses

An example of the PROC MIXED code is provided below:

For the primary objective – relative BA (B,C,D vs A):

proc mixed data=tab.pk; class seq period trt participant; model l&var=seq period trt/ ddfm=KR; random participant(seq) /subject=participant(seq); lsmeans trt; estimate 'B vs A' trt -1 1 0 0 0 /cl alpha=0.1; estimate 'C vs A' trt -1 0 1 0 0 /cl alpha=0.1; estimate 'D vs A' trt -1 0 0 1 0 /cl alpha=0.1;

> ods 'Estimates' out=est&var; ods 'Ismeans' out=Is&var; ods 'covparms' out=cov&var; ods 'tests3' out=tst&var;

run;

For the primary objective – relative BA (E vs A):

proc mixed data=tab.pk;

class seq trt participant; model l&var=seq trt/ ddfm=KR; random participant(seq) /subject=participant(seq); lsmeans trt; estimate 'E vs A' trt -1 0 0 0 1 /cl alpha=0.1;

ods 'Estimates' out=est&var; ods 'lsmeans' out=ls&var; ods 'covparms' out=cov&var; ods 'tests3' out=tst&var;

run;

/* Letter assignments for treatments (trt) within the estimate statement above are as follows Treatment A: Single oral dose of etrasimod 2 mg clinical IR tablet under fasted conditions (Reference)

Treatment B: Single oral dose of etrasimod 2 mg mini tablets mixed with applesauce under fasted conditions (Test 1)

Treatment C: Single oral dose of etrasimod 2 mg mini tablets mixed with chocolate pudding under fasted conditions (Test 2)

DMB02-GSOP-RF02 7.0 Statistical Analysis Plan Template 31-Jan-2022 PFIZER CONFIDENTIAL TMF Doc ID: 98.03 Page 17 of 20 Treatment D: Single oral dose of etrasimod 2 mg mini tablets mixed with water under fasted conditions (Test 3)

Treatment E: Single oral dose of etrasimod 2 mg mini tablets mixed with yogurt under fasted conditions (Test 4) */

Abbreviation	Term
%CV	coefficient of variation
AA	alopecia areata
AD	atopic dermatitis
AE	adverse event
AUC _{extrap} %	the percent of AUC _{inf} based on extrapolation
AUC _{inf}	area under the plasma concentration-time profile from time zero extrapolated to infinite time
AUC	
AUC _{last}	area under the plasma concentration-time profile from time zero to the time of the last quantifiable concentration
BA	bioavailability
BLQ	below the limit of quantitation
BP	blood pressure
CaPS	Clinical Data Interchange Standards Consortium and Pfizer Standards
CD	Crohn's Disease
CI	confidence interval
Clast	last quantifiable concentration
CL/F	apparent clearance after oral dose
C _{max}	maximum plasma concentration
CSR	clinical study report
ECG	electrocardiogram
EoE	eosinophilic esophagitis
HR	heart rate
IR	immediate-release
kel	terminal phase rate constant
LLQ	lower limit of quantitation
mg	milligram
ms	millisecond
N/A	not applicable
NC	not calculated
ND	not done
NS	no sample
PD	pharmacodynamic(s)
РК	pharmacokinetic(s)
PR	pulse rate
PR interval	time from the beginning of the P wave to the beginning of the QRS
	complex
QRS	Combination of Q-, R- and S- wave on an electrocardiogram representing
	ventricular depolarization
QTc	corrected QT
QTcF r ²	corrected QT (Fridericia method)
r^2	goodness of fit statistic from the log-linear regression

Appendix 2. List of Abbreviations

Abbreviation	Term
rBA	relative bioavailability
RR	the time between the start of one QRS complex and the start of the next
	QRS complex
SAP	statistical analysis plan
SD	standard deviation
S1P	sphingosine 1-phosphate
S1P _{1,4,5}	S1P receptors 1, 4, and 5
SoA	schedule of activities
t _{1/2}	terminal elimination half-life
TEAE	treatment emergent adverse event
T _{max}	time for C _{max}
UC	ulcerative colitis
V_z/F	apparent volume of distribution after oral dose

DMB02-GSOP-RF02 7.0 Statistical Analysis Plan Template 31-Jan-2022 PFIZER CONFIDENTIAL TMF Doc ID: 98.03 Page 20 of 20
